Estimation of sample size is based on the aim of this study to detect the sensitivity (i.e., true positives) and specificity (i.e., true negatives), as well as 1-sensitivity (false positives) and 1-specificity (i.e., false negatives) in order to characterize the ability to correctly diagnose patients with cCR with a minimum of regrowth (i.e., false negatives) or unnecessary resections (i.e., false positives). Based on these estimations, it will be possible to achieve the primary endpoint of the study, i.e. the rate of regrowth, and to calculate positive predictive value of the diagnosis of cCR among patients who follow the W&W protocol after preoperative chemoradiotherapy.

As the present study is a prospective observational study, and not a clinical trial that aims to prove the superiority or non-inferiority of a specified treatment, power calculations that result in *numbers needed to treat or to harm*, do not apply here for the estimation of number of patients to include.

By including patients into the study who wish to undergo surgical resection despite the clinical finding of cCR, and decide not to follow the W&W algorithm, it will be possible to calculate these parameters based on a 2x2 table on the following assumptions based on results from current literature:

- During this time period, a tenfold/approx. 1000 patients will receive neo-adjuvant treatment
- Of those, 100 patients with cCR to enter the W&W protocol
- Of those 100, it may be assumed that
 - 85 will have a true CR
 - 15 will have ypCR (i.e., ypT0) after surgical resection
 - of those 100 patients, up to 30 may have regrowth after initial cCR within the W&W protocol
- Finally, 900 of 1000 (i.e., 870 patients + 30 patients with regrowth) will have ypT1-4 after surgical resection

Accordingly, the study aims to include at least 100 patients with cCR who choose to follow the W&W algorithm.

	True CR	No CR	
W&W (cCR)	True positive N=85	False positive N=30 (regrowth)	115
No W&W (No cCR)	False Negative N=15	True Negative N=870	885
	100	900	1000

Based on these figures, it will be possible to calculate sensitivity, specificity, 1-sensitivity, 1-specificity, positive and negative predictive values, positive and negative likelihood ratios, and perform ROC curve analysis.

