The study will include patients until a number of 100 patients has been entered the W&W protocol. Taking into account that 70% of all eligible patients with cCR patients will be identified, i.e. annually 31/50 will be included nationwide, an inclusion period of at least three years will be needed to achieve the goal of 100 study participants. Taking into account that some patients will reject participation in the study and/or decide to withdraw, or be lost to follow-up by other reasons, an inclusion period of up to 5 years might be necessary to achieve the inclusion goal.

One year after start of inclusion, the steering group will evaluate the recruitment with regard to the feasibility of the inclusion goal.

Data collection

Data collection will include clinically relevant variables that are part of common clinical practice independently of the cCR protocol, and that are part of the mandatory public registries (i.e., CRN and NCCR), such as:

- Patient characteristics
- Tumour characteristics (clinical, imaging, pathological and biological), values of blood tests
- Data on oncological treatment (radiation, chemotherapy)
- Surgical procedures
- Pathology reports
- Follow-up data, including possible regrowth, recurrence and metastases, and survival
- PROMs

Data will be collected and recorded at every patient visit and assessment. Given the limited number of patients, data will be collected on paper sheets temporarily at every participating study site under secure circumstances. After one year of inclusion a first interim analysis of all cases will be performed, and data entered into a suitable database provided by the NCCR.

Coupling with other national databases

To enhance data quality, or to increase the information available in the dataset, it will be useful to couple the current dataset with other national registries:

- Norwegian Patient Registry
- Cancer Registry of Norway
- Norwegian Colorectal Cancer Registry
- Norwegian Quality Registry for Gastro-intestinal Surgery (NoRGast)
- The Norwegian Prescription Database

The patients will be asked to consent to coupling to those registries. The study protocol requires the possibility to use indirectly identifiable data due to the coupling of databases.

Statistics

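### The planning bullets and the 2x2 table in the sample-size section cannot all hold, so the planned regrowth rate and PPV are ambiguous (26.1%, up to 30%, or 15% regrowth)

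*Protocol*

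**What the plan says.** All of this is in the Protocol, mostly in Study population and sample size.

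- Starting population: "approx. 1000 patients will receive neo-adjuvant treatment".
- Entry to W&W: "Of those, 100 patients with cCR to enter the W&W protocol".
- Three statements about those 100: "85 will have a true CR"; "15 will have ypCR (i.e., ypT0) after surgical resection"; and "of those 100 patients, up to 30 may have regrowth after initial cCR within the W&W protocol".
- Patients without complete response: "900 of 1000 (i.e., 870 patients + 30 patients with regrowth) will have ypT1-4 after surgical resection".
- The 2x2 table: the W&W (cCR) row has 85 true positives and, in the next cell, "False positive N=30 (regrowth)", with a printed total of 115. The row without W&W has 15 false negatives and 870 true negatives, total 885. The column totals are 100 (true CR) and 900 (no CR).
- Target: the text after the bullets aims for at least 100 W&W patients. The same section then says: "The study will include patients until a number of 100 patients has been entered the W&W protocol". Time schedule repeats that inclusion ends at 100.

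Under Objectives and endpoints, the primary endpoint is the regrowth rate in W&W patients, used to determine the PPV of cCR. The sample-size section says that power calculations do not apply. It gives no precision target and rests the number of patients on these assumptions and this table.

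**The concern.** The regrowth rate and the PPV are both read from a single row, the patients who enter W&W. The table places true CR and regrowth in opposite columns of that row, so one patient cannot count as both. Yet 85 and 30 are both drawn from 100 patients, and the table makes room for them only by enlarging the row to 115.

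The figure 100 thus plays two parts. In the bullets and the inclusion rule it is the number entering W&W, a row total. In the table it is the number with true CR, a column total. The 15 patients with pathological complete response change place as well: they are listed among the W&W entrants but tabulated outside W&W.

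With no other basis given for the sample size, a reader cannot tell what regrowth rate or PPV the study was planned around, or with what precision 100 patients would estimate it.

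**Working it through.** **Inputs** (Protocol, Study population and sample size): about 1000 treated; 100 entering W&W; of those, 85 true CR, 15 pathological CR after resection, up to 30 regrowths; 900 = 870 + 30 without CR. Table cells: TP 85, FP 30, FN 15, TN 870.

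**Step 1. Reproduce the printed table.** Rows: 85 + 30 = 115 and 15 + 870 = 885. Columns: 85 + 15 = 100 and 30 + 870 = 900. Total: 1000. The table is internally consistent, and its no-CR column agrees with the 870 + 30 = 900 bullet. The 115 is therefore not a fault of text extraction.

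**Step 2. Compare with the bullets.** The W&W row should be 100; the table has 115. If 30 of 100 regrow, at most 100 − 30 = 70 are true CR, not 85. If 85 of 100 are true CR, at most 100 − 85 = 15 can regrow, not 30.

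**Step 3. Planned primary endpoint on each basis.** Regrowth = FP/(TP + FP) and PPV = TP/(TP + FP) = 1 − regrowth. Exact (Clopper-Pearson) 95% limits for x of n are the 2.5% quantile of Beta(x, n − x + 1) and the 97.5% quantile of Beta(x + 1, n − x).

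| Basis | Regrowth | Exact 95% CI | PPV |
|---|---|---|---|
| Printed table | 30/115 = 26.1% | 18.3–35.1% | 85/115 = 73.9% |
| Regrowth bullet, 30 of 100 | up to 30/100 = 30.0% | 21.2–40.0% at 30/100 | at least 70.0% |
| True-CR bullet, 85 of 100 | 15/100 = 15.0% | 8.6–23.5% | 85.0% |

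**Step 4. Tables that are consistent with a W&W row of 100.** The second row is 900 in each case. Sensitivity = TP/(TP + FN); specificity = TN/(TN + FP).

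| Option | TP | FP | FN | TN | Columns | Sensitivity | Specificity |
|---|---|---|---|---|---|---|---|
| A1: 30 regrowths, FN kept at 15 | 70 | 30 | 15 | 885 | 85 / 915 | 70/85 = 82.4% | 885/915 = 96.7% |
| A2: 30 regrowths, columns kept | 70 | 30 | 30 | 870 | 100 / 900 | 70/100 = 70.0% | 870/900 = 96.7% |
| B: 85 true CR | 85 | 15 | 15 | 885 | 100 / 900 | 85/100 = 85.0% | 885/900 = 98.3% |

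The printed table gives sensitivity 85/100 = 85.0% and specificity 870/900 = 96.7%.

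**Step 5. What each option does to the 870 + 30 = 900 bullet.** A1 changes it to 885 + 30 = 915. A2 leaves it as it is. B changes it to 885 + 15 = 900. A repair that alters only the table may therefore create a new conflict with that bullet.

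**The case against.** The strongest defence is that the table is right and one bullet is badly worded: 100 would be the number with true CR (85 in W&W and 15 found at surgery), and 115 the number in W&W. This keeps the 870 + 30 = 900 bullet, and 100 of 1000 agrees with the 10% pathological CR frequency cited in Background. It does not resolve the matter. The text says that the 100 enter W&W, derives a W&W target of 100 from this, and ends inclusion there. On this reading, a column total has been carried into the enrolment target.

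A second defence is that 30 is a ceiling. Taken alone, 85 true CR and 15 regrowths respect both of those bullets, and the table's 26.1% is also below 30%. That stands as far as the rates go. But the table and the 900 bullet use the full 30 beside 85, which is what gives a row of 115.

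A third is that little depends on it. The study is observational, tests no hypothesis, and will estimate regrowth from observed data. This also stands, and it limits the consequence.

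Some stronger readings are tempting but unsupported:

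- A reader might infer that 70/30/15/885 is the correct table, because 70 + 15 gives back the 85. The documents list 85 and 15 separately and the table adds them to 100, so the match proves nothing.
- A reader might infer a planned regrowth rate of 30%. The text gives that only as an upper bound.
- A reader might infer that the plan enrols exactly 100. One sentence says at least 100, although the inclusion rule, stated twice, stops at 100.

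**Conclusion.** The contradiction holds, and it lies in figures that the Protocol itself states. The bullets, the table and the inclusion rule cannot all be true together. The planned regrowth rate is 26.1%, at most 30%, or 15%, depending on which figure is taken; the corresponding PPV is 73.9%, at least 70%, or 85%. The span from 15% to 30% is a factor of two in the planning value of the primary endpoint.

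This rests on two assumptions: true CR and regrowth are mutually exclusive, as the table treats them, and the W&W row is the denominator for the regrowth rate and PPV, as the primary endpoint defines it.

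A reader might go further and infer that the study is 15 patients short or that its analysis will be wrong. The documents do not support either. No precision requirement is derived from the table, so 115 was never a stated need, and the analysis will use observed counts. The effect is on the stated rationale and the planned precision. Why 100 ended up in two places is a matter of inference, and which reading was intended cannot be decided from the text.

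**What to change.** By amendment, the sponsor should:

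1. State whether 100 is the number entering W&W or the number with true CR. Since inclusion stops at 100 W&W patients, the W&W row should total 100.
2. Say which group the 15 patients with pathological CR belong to.
3. Rebuild the bullets, including the 870 + 30 = 900 bullet, and the table together. Options A1, A2 and B above are each internally consistent. The choice is the sponsor's and should be justified from the literature on which the assumptions rest.
4. Restate one planned regrowth rate and PPV with an exact 95% CI at n = 100, for example 21.2–40.0% at 30 regrowths or 8.6–23.5% at 15. If 30 is kept, it should be labelled as an upper bound.
5. Align the wording of the target (at least 100) with the rule that ends inclusion at 100.

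The cost is a correction to text and table. It needs no extra patients and no change to the enrolment target. Depending on the option, the stated PPV becomes at least 70% or 85% instead of the table's 73.9%, and the stated sensitivity becomes 82.4% or 70.0% or stays at 85.0%.

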The main problem is how to detect those tumours that are radiosensitive and will be highly likely to result in CR by CRT only, thus eliminating the need for major surgical resections with

considerable surgical morbidity and impairment of functions, in addition to late postradiation effects.

cCR is currently defined by the four clinical characteristics as described by the Habr-Gama group. At present, it remains unclear whether the additional use of Magnetic Resonance Imaging (MRI) may increase the predictive value of cCR, and conflicting results are reported (18, 19). This may, however, change with future improvements of diagnostic imaging tools and protocols. Further, tissue sampling during observation after CRT has currently no place in enhancing the sensitivity or specificity of cCR (15). Moreover, there are at present no molecular or other tumour characteristics that can predict CR.

According to the Norwegian guidelines – like others – the recommended waiting time before surgery is at least 6 -8 weeks, and up to 10-12 weeks after CRT. A waiting time of 12-13 weeks after long course CRT in tumours that respond is associated with an increased rate of cCR without any impaired prognosis (20). Thus, tumours with a near cCR at 6-8 weeks might result in a cCR at 12-13 weeks, and the patients who do not achieve cCR after 12-13 weeks and then undergo surgery will according to current knowledge not have inferior prognosis compared to those operated at 6 -8 weeks.

There are only a few studies in the literature that report on more than 50 – 100 patients in single centre series (21, 22). Due to the nature of the disease and treatment, such studies are not easy to conduct. Furthermore, the inclusion and exclusion criteria used in the various studies differ considerably, and the study populations are heterogeneous. The protocols vary with regard to the use of CRT and the waiting time for assessment of the response. Therefore, studies based on population based registries, such as the Cancer Registry of Norway or the Norwegian Colorectal Cancer Registry, are highly likely to provide important information.

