The W&W has gained great interest, as it provides the possibility to cure the patients without the need of major surgery and its consequences on functional outcomes and lifelong morbidity, and thus preventing overtreatment. However, this treatment concept is currently regarded as experimental and has not yet become part of commonly accepted guidelines. There is a need to increase the knowledge on the concept of cCR and CR in a population based patient cohort with a standardized treatment algorithm and follow-up.

Aim of the study

The aim of this study is to estimate the rate of regrowth among patients with locally advanced rectal cancer treated with neoadjuvant treatment with radiotherapy or chemoradiotherapy, where complete clinical response has been obtained, and thus to determine the positive predictive value of cCR in a national cohort.

Objectives and endpoints

Primary endpoint is the *rate of regrowth* among patients with cCR who follow the W&W protocol after preoperative radiotherapy or chemo-radiotherapy, in order to determine the positive predictive value of cCR.

Secondary endpoints are

- The rate of cCR after preoperative CRT
- To calculate the diagnostic accuracy of the clinical diagnosis of complete response
- The rate of metachronous distant metastases in patients following the W&W protocol
- The rate of metachronous metastasis and recurrence rate after ypCR
- Overall and cancer-specific survival of patients with cCR following the W&W protocol compared to patients with ypCR, i.e. patients with complete pathologic response after resection.
- Assess the rate of patients who otherwise would have had an APR
- Patient-reported outcome measures, such as Low anterior resection syndrome (LARS) and quality of life (QoL)
- To calculate the costs of treatment for W&W after cCR as compared to surgical treatment
- To assess the diagnostic accuracy of MRI in the diagnosis of complete response

Design

The current study is designed as an open prospective population-based study. All patients diagnosed and treated with radiotherapy or chemo-radiotherapy for rectal cancer in Norway will be eligible for this study, provided signed informed consent given before inclusion.

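### The planning 2x2 table counts W&W patients without regrowth and operated patients with ypT0 as one True CR group, so the planned sensitivity, specificity and likelihood ratios refer to neither target condition

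*Protocol*

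**What the plan says.** The Study population and sample size section builds its table from these planning assumptions:

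- Cases called cCR and confirmed: "85 will have a true CR".
- Cases called cCR and not confirmed: "of those 100 patients, up to 30 may have regrowth after initial cCR within the W&W protocol".
- Complete responses found at operation: "15 will have ypCR (i.e., ypT0) after surgical resection".
- The rest: "Finally, 900 of 1000 (i.e., 870 patients + 30 patients with regrowth) will have ypT1-4 after surgical resection".

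The printed cells are 85 true positives, 30 false positives (marked as regrowth), 15 false negatives and 870 true negatives. The section then states: "Based on these figures, it will be possible to calculate sensitivity, specificity, 1-sensitivity, 1-specificity, positive and negative predictive values", followed by likelihood ratios and ROC analysis. The corresponding secondary endpoint under Objectives and endpoints is: "To calculate the diagnostic accuracy of the clinical diagnosis of complete response".

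The two rows are verified at different times. W&W patients are followed for up to 8 years (W&W schedule; Time schedule). Patients with near-cCR who do not reach cCR at the second assessment, at about 12 weeks, go to surgery then (W&W inclusion criteria; Response evaluation before enrolment in the study). The protocol names no common reference standard or time horizon for a true complete response and does not mention the difference between the rows.

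**The concern.** The clinical call decides which reference standard a patient receives, which is differential verification. For a patient called cCR, a true complete response means no regrowth over years. For a patient not called cCR, it means no tumour in a specimen taken within months. These can disagree both ways. A tumour with residual cells at resection might have gone on to a lasting response, and a ypT0 case might not have stayed clear had the rectum been left in place.

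Sensitivity divides the 85 by a total made of both kinds of case, so it estimates neither the share of lasting responders detected nor the share of pathological responders detected. Specificity and the likelihood ratios carry the same mixture. Because 870 operated test-negatives stand beside only 100 counted as true CR, reclassifying a few of them shifts sensitivity noticeably. A national cohort could then report a precise-looking accuracy figure that readers cannot interpret.

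**Working it through.** **Inputs.** TP = 85, FP = 30, FN = 15 and TN = 870, all from the printed table. The protocol gives no figures for the next two quantities, so both are assumptions:

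- x = resected ypT1-4 tumours that would have become a lasting complete response.
- y = resected ypT0 cases that would not have lasted.

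**Reproducing the table.** 85 + 30 = 115; 15 + 870 = 885; 85 + 15 = 100; 30 + 870 = 900; total 1000. The margins agree with print. The protocol prints no accuracy values. The cells imply those in the first row of the table below, with PPV = 85/115 = 73.9%.

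**One target condition throughout.** Take lasting complete response as the target. The W&W row is already judged that way and stays fixed. In the other row, x moves from TN to FN and y from FN to TN:

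- Sensitivity = 85/(100 + x - y)
- Specificity = (870 - x + y)/(900 - x + y)
- NPV = (870 - x + y)/885
- LR+ = sensitivity/(1 - specificity); LR- = (1 - sensitivity)/specificity

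| x, y (assumed) | Sensitivity | Specificity | NPV | LR+ | LR- |
|---|---|---|---|---|---|
| 0, 0 (as printed) | 85/100 = 85.0% | 870/900 = 96.7% | 870/885 = 98.3% | 25.5 | 0.155 |
| 9, 0 (x about 1% of 870) | 85/109 = 78.0% | 861/891 = 96.6% | 861/885 = 97.3% | 23.2 | 0.228 |
| 44, 0 (x about 5% of 870) | 85/144 = 59.0% | 826/856 = 96.5% | 826/885 = 93.3% | 16.8 | 0.425 |
| 0, 5 | 85/95 = 89.5% | 875/905 = 96.7% | 875/885 = 98.9% | 27.0 | 0.109 |
| 0, 15 | 85/85 = 100% | 885/915 = 96.7% | 885/885 = 100% | 30.5 | 0 |

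PPV stays at 73.9% throughout. Sensitivity is overstated when x > y, understated when y > x, and unchanged when they are equal.

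**Dependence on the baseline.** The printed cells conflict with the text. The table's cCR row holds 115 patients, while the text has 100 entering W&W with up to 30 regrowths. That leaves 70 without regrowth, not 85. With cells 70/30/15/885 (total 1000), sensitivity = 70/(85 + x - y): 70/85 = 82.4% at baseline, 70/94 = 74.5% at x = 9, 70/129 = 54.3% at x = 44, and 70/80 = 87.5% at y = 5. The pattern is the same.

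**The case against.** Several counter-arguments are sound.

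- **The false positives also get a specimen.** The protocol expects the 30 regrowths to be ypT1-4 at resection, so the No CR column rests on histology in both rows and differs mainly in timing. This stands. The clear mixing is in the True CR column, and specificity stays between 96.5% and 96.7% in the table above.
- **PPV and NPV.** A reader might infer that these mix targets as well. They do not. The section ties PPV to patients who follow W&W, and both NPV cells (15 and 870) come from specimens. NPV does, however, answer a different question from the regrowth-based PPV.
- **Continuing regression.** A reader might infer from the Background that resected tumours were still regressing, so that sensitivity must be overstated. The text says only this: "A waiting time of 12-13 weeks after long course CRT in tumours that respond is associated with an increased rate of cCR". It is limited to responding tumours and says nothing about the time after 13 weeks. Near-cCR patients also get a second assessment at about 12 weeks and enter W&W if they reach cCR. The pull from ypT0 cases that would not have lasted goes the other way.
- **The size is assumed.** The documents give neither x nor the number of near-cCR patients. Applying a percentage to all 870 includes poor responders, for whom the Background gives no support for a late response. The figures are a stress test, not estimates.
- **It cannot be avoided in practice.** Verifying every patient by one standard is not feasible here, and this is a planning table. That makes the point one of reporting. But the protocol itself says which measures come from the table, so it is more than a detail left to a later analysis plan.

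**Conclusion.** The concern holds in a limited form. The table adds two target conditions under True CR. The sensitivity, specificity and likelihood ratios planned from it therefore lack a single meaning, and this affects a secondary endpoint. The practical effect falls on sensitivity and the likelihood ratios.

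Under the assumed values, sensitivity runs from 59.0% (x = 44) to 89.5% (y = 5) around the printed 85%, and reaches 100% if none of the 15 ypT0 cases had lasted. The documents fix neither x nor y, so they support no direction of bias. The 85% is itself not a firm baseline because of the conflict between 115 and 100; the alternative is 82.4%. The primary endpoint (regrowth rate in W&W) and the PPV taken from W&W patients are untouched. The plan should be changed on this point, but the study's main result does not depend on it.

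**What to change.** Amend Study population and sample size, and Statistics, as follows:

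1. Keep the regrowth rate and PPV from W&W follow-up, as already planned.
2. For operated patients, report ypT0 versus ypT1-4 separately by clinical call: cCR but declined W&W, near-cCR, no cCR. Show those who declined as their own test-positive group. The table's second row equates being outside W&W with having no cCR and leaves them no cell. Also report by interval from radiotherapy to surgery where dates are recorded.
3. If a combined sensitivity, specificity or likelihood ratio is still given, label it as based on a mixed reference standard and show a range over x and y in both directions.
4. Reconcile the 115 in the table with the 100 in the text before quoting any baseline.

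The cost is mainly wording, and no patient's care changes. Two checks are needed. Data collection lists treatment, surgery and pathology but does not name dates. The protocol also asks patients considered for cCR to have their data recorded, so it should be confirmed that data exist for the remaining operated patients. The downside is that a single accuracy figure becomes a range or two separate reports.

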For analysis of the study, standard descriptive and analytic statistics will be applied when appropriate, and according to the distribution of the various variables. Multivariable analyses will be performed when appropriate with regard to relevant outcome variables, and in order to detect independent predictors of the outcome in question.

Survival analyses will be performed by Kaplan-Meier estimates and factors compared by using the log rank test. Multivariable analysis for time-dependent outcomes will be performed by Cox proportional Hazards analysis in order to detect independent predictors of the outcome in question.

The steering group has the necessary statistical knowledge and competency to provide appropriate statistic evaluation and analysis.

Organization

Patients with rectal cancer will be treated at all Norwegian hospitals that offer diagnosis and treatment for rectal cancer within the public specialist health service and according to national regulations and guidelines. When evaluation at 6 weeks after completed radiation indicates a possible full or near cCR, the patient will be referred to the cooperating University Hospital for further evaluation and recruitment to the W&W protocol when indicated, and informed consent will be obtained.

At each University Hospital, two dedicated colorectal surgeons will examine these patients, include in the W&W protocol and perform follow-up as described according to commonly agreed definitions. They will maintain the data entry forms and registration at the national registries.

In the case of equivocal or uncertain findings, these will be discussed in a collegial forum to achieve consent and decisions.

The W&W protocol will be referred to in the national guidelines as an ongoing study, and thus represent a treatment within a scientific study protocol. The study will be registered on public Norwegian websites such as <https://kliniskestudier.helsenorge.no>, and will be registered at clinicaltrials.gov.

Costs, finances and resources

The W&W protocol will be performed within the public specialist health care. Examinations that are part of the W&W protocol are mostly inexpensive clinical examinations or routine blood tests, with the exception of MRI examinations. However, the number of study participants is low, and as included patients will not need hospital consumptions related to surgery, the total economic load of the study is considered to be low.

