The study group will apply for grants for financial support in order to cover expenses that are not covered by public health funding, such as development of CRF and study database, other costs related to collection of necessary data or information, research time for analysis, preparation of manuscripts and publication, including participation in international meetings, and if necessary, costs for supplemental data from other registries.

Insurance

Patients entering the W&W protocol will be covered by the ordinary liability insurance of the respective health trust and NPE (Norsk pasientskade erstatning) in line with any specialist health service. Every institution has the responsibility for its patients in line with relevant Norwegian legislation for specialist health care. Therefore, there will be no need for other insurances.

Time schedule

Recruitment will start as soon as possible when all permissions according to Norwegian law are obtained. The inclusion time will end when 100 W&W patients have enrolled the study, which is estimated to three to five years. Patients will be followed for 8 years.

Publication

The results will be published in international journals on behalf of the NGICG-CR. The writing group will consist of the persons as defined above, and the Vancouver guidelines and journal policies will apply. Results will be published regardless of the outcomes.

Ethical considerations

cCR is documented in scientific literature and applies for about 10, and maybe up to 20% of the patients. There is, albeit limited, evidence in the literature that a considerable proportion of patients with cCR followed with watchful waiting do fare well, and that treatment outcomes in patients operated on for tumour regrowth do achieve comparable results with regard to local recurrence and survival.

Current standard of surgical treatment, i.e. rectal resection or amputation, induces considerable short- and long-term comorbidity (surgical complications; low anterior resection syndrome, permanent stoma, chronic pain, bladder dysfunction, sexual dysfunction, or other injury of pelvic organs etc.), and may even lead to death. Thus, as a certain group of patients might be treated sufficiently with oncological treatment alone, these patients will possibly be subjected to over-treatment and may, thus, possibly be harmed by surgery. Moreover, avoidance of surgery after cCR will preserve rectal function and thus avoid a permanent colo- or ileostomy in those patients.

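### Cancer-specific survival is assigned to Kaplan-Meier, which overstates the absolute risk of cancer death when other-cause deaths are censored; cumulative incidence should be reported with it

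*Protocol*

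**What the plan says.** Under Objectives and endpoints, one secondary endpoint is "Overall and cancer-specific survival of patients with cCR following the W&W protocol compared to patients with ypCR". Overall and cancer-specific survival therefore appear together, for the same two groups.

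The Statistics section gives one method for both: "Survival analyses will be performed by Kaplan-Meier estimates and factors compared by using the log rank test". The next sentence adds that "Multivariable analysis for time-dependent outcomes will be performed by Cox proportional Hazards analysis". It does not separate overall from cancer-specific survival, and it names no competing-risk estimator. The protocol does not define a cancer-specific death, give a censoring rule, or say how a postoperative death is classified.

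Under Time schedule, "Patients will be followed for 8 years". Under Study population and sample size, "the study aims to include at least 100 patients with cCR who choose to follow the W&W algorithm", and the study is described as "not a clinical trial that aims to prove the superiority or non-inferiority of a specified treatment". Accordingly, no event rate, hazard ratio or power figure is given for survival. Ethical considerations says of resection that it "may even lead to death".

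**The concern.** Kaplan-Meier is right for overall survival, because every death is an event. For cancer-specific survival, a death from another cause prevents a later cancer death. If such deaths are censored, one minus the curve estimates the risk of cancer death in a hypothetical population in which nobody dies of anything else. That is always at least as large as the proportion who actually die of cancer.

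The gap grows with other-cause mortality and with time, so a horizon of up to 8 years makes it more visible. A clinician or patient weighing watch and wait against resection would probably read the curve as an absolute risk, and for that purpose it is too high. The excess in each group depends on that group's own other-cause mortality.

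**Working it through.** **No figure to reproduce.** The protocol states no survival rate, so what follows is an illustration. Its rates are assumptions, shown over a range.

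**Inputs.** From the protocol: an 8-year horizon and at least 100 watch-and-wait patients. Assumed: constant hazards λc (cancer death) and λo (other death). Net risk means the risk of one cause if the other did not operate.

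**Formulas at time T.**
- 1−KM = 1 − exp(−λc·T)
- Cumulative incidence (CIF) = λc/(λc+λo) × [1 − exp(−(λc+λo)·T)]

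**Set A: net 8-year risks.** Cancer 15%, so 8λc = −ln 0.85 = 0.1625.
- Other causes 15%: CIF = 0.5 × (1 − 0.85 × 0.85) = 13.9%. Excess 1.1 points.
- Other causes 30% (8λo = 0.3567): CIF = 0.1625/0.5192 × (1 − 0.85 × 0.70) = 12.7%. Excess 2.3 points.

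Cancer 20%, so 8λc = 0.2231.
- Other causes 15%: CIF = 18.5%. Excess 1.5 points.
- Other causes 30%: CIF = 16.9%. Excess 3.1 points.

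**Set B: net 5-year risks carried to 8 years**, with 8λ = −1.6 × ln(1 − 5-year risk). Excesses are from unrounded values.

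| Cancer, 5 y | Other, 5 y | 1−KM, 8 y | CIF, 8 y | Excess (points) |
|---|---|---|---|---|
| 5% | 5% | 7.9% | 7.6% | 0.3 |
| 5% | 10% | 7.9% | 7.3% | 0.6 |
| 5% | 20% | 7.9% | 6.6% | 1.2 |
| 10% | 5% | 15.5% | 14.9% | 0.6 |
| 10% | 10% | 15.5% | 14.3% | 1.2 |
| 10% | 20% | 15.5% | 13.1% | 2.4 |

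Read at 5 years instead, the same inputs give an excess of 0.1 to 1.0 points.

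**Postoperative deaths.** Add an assumed share d of 1% to 5% dying straight after surgery in the ypCR group, with net 5-year risks of 10% for each cause and equal cancer hazards in both groups. For simplicity no surgical deaths are placed in the watch-and-wait group. At 8 years:
- Those deaths censored: 1−KM is 15.5% in both groups.
- Those deaths counted as cancer-specific events: ypCR becomes 1 − (1−d) × (1 − 0.155), or 16.4% to 19.7%.
- CIF of cancer death: 14.3% in watch and wait, and (1−d) × 14.3%, or 14.2% to 13.6%, in ypCR.

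So classification decides how these deaths appear. Changing the estimator alone does not bring them into the cancer-death curve.

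**Sampling error, for scale.** At 15% in 100 patients, the binomial standard error is √(0.15 × 0.85/100) = 3.6 points.

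**The case against.** The endpoint asks for a comparison, and with other deaths censored the log-rank test and Cox model compare cause-specific hazards legitimately. The overstatement is smaller than one standard error in 100 patients. If other-cause mortality is similar in the two groups, it largely cancels in their difference. Every rate is assumed. Definitions and censoring rules are commonly left to a statistical analysis plan, which may exist and is not shown here.

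Most of this stands, and it keeps the point small. It does not remove it: the protocol is not silent on the estimator but assigns Kaplan-Meier to all survival analyses. The bias also runs in one direction and does not shrink with more patients. The missing cause-of-death definition is not counted as a fault here.

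A reader might infer more than the protocol supports:
- *That Kaplan-Meier with log-rank is the only method named.* Cox regression follows in the next sentence. It would normally censor other deaths too, so it supplies no absolute risk.
- *That operative deaths are censored and so hidden from the study.* No rule says so, and they could be counted as events. Overall survival, compared in the same endpoint, counts every death.
- *That the comparison sets surgery against no surgery.* The sample-size section allows for regrowth in as many as 30 of 100 watch-and-wait patients, and the Design section plans resection for regrowth.
- *That the same error affects metachronous metastases.* That endpoint is called a rate and has no named estimator, so using cumulative incidence there is only a suggestion.

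**Conclusion.** The point holds as a minor one about a secondary endpoint. If non-cancer deaths are censored in the usual way, the stated Kaplan-Meier curve for cancer-specific survival overstates the absolute 8-year probability of cancer death by roughly 0.3 to 3 percentage points. That size rests on constant hazards, net 8-year cancer mortality of about 8% to 20%, and net other-cause mortality of about 8% (5% at 5 years) to 30%. The protocol supplies none of these rates. The between-group tests of cause-specific hazard are not invalidated, and overall survival is unaffected.

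**What to change.** In Statistics, separate the two survival endpoints:
- Overall survival: Kaplan-Meier, as now.
- Cancer-specific survival: report the cumulative incidence of cancer death by the Aalen-Johansen estimator, with other-cause death as a competing event. Keep log-rank and Cox, described as comparisons of the cause-specific hazard.
- Show treatment-related death as its own category in both groups, because watch-and-wait patients resected for regrowth are also exposed to it. This needs a short rule for assigning cause of death.
- Present these results beside overall survival, so that all deaths are visible together.

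This costs a sentence or two and a standard extra analysis. The small downside is one more curve per group to report. No patient procedure, visit or sample size changes.
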